### **Pain Measurement**

Visual Analog Scale was used to assess the subjects' pain during rest and activity. A 10 cm line was drawn and subjects were wanted to mark the point (0; no pain, 10; worst imaginable pain) as representing the pain during rest and activity (18).

### **Muscle Strength Measurement**

Quadriceps, hamstring muscles and the hip stability isometric test (HipSIT) strength were measured with a hand-held digital dynamometer (Lafayette Instrument Company, Lafayette). Each subject was verbally informed before the test in order to ensure correct movement and subjects were asked to perform submaximal contraction against the evaluator's hand before testing (19). "Break test" technique was performed for the strength measurement. According to this technique, the evaluator gradually overcomes the muscle strength and stops when the joint gives way (20). The quadriceps muscle strength was measured in a sitting position (Hip 90° flexion, knee extended) with hands crossed across the chest. The hand-held dynamometer was positioned on the anterior surface of the lower leg proximal to the ankle during test (21). Hamstring muscle group measurement was carried out on prone position (Hip neutral position, knee flexion 90°). The hand-held dynamometer was positioned on the posterior surface of the lower leg proximal to the ankle during test (21). The HipSIT evaluates the abductor, external rotator and extensor muscles of the hip together. This test was performed in a side-lying position (Hips 45° flexion, knees 90° flexion, heels in contact with the limb tested superior to opposing limb as 20° abduction). The hand-held dynamometer was placed on laterally positioned 5 cm above the knee joint interline during test (22). Each measurement for each muscle was performed 3 times at 30 sec intervals and the higher value was recorded. There was also a minute interval between muscle groups measurements.

### **Functional Performance Measurement**

A 30-sec chair stand test and stair climb test were used to assess physical performance. The subjects were asked to stand up from a chair (height: 43cm) and sit down in 30 sec with their arms folded across the chest during the 30-sec chair stand test. The number of the repetitions were recorded (23). The subjects were asked to ascend and descend 10 steps (step height 20 cm) at a safe and comfortable pace during the stair climb test. The time (sec) of stair ascend and descend were recorded separately (24).

### **Functional Status**

The Western Ontario and McMaster Universities (WOMAC) index is a disease specific self-administered test for OA to assess functions of the affected joints. It consists of 24 questions

(three subscale; pain (5 questions), stiffness (2 questions) and daily activities (17 questions) (25).

### **Interventions**

Each subject was informed about knee OA and daily activities that negatively affect the knee OA. They were also asked to use cold press 3 times (10-15 min) a day for 6 weeks. Supervised physiotherapy group performed exercises 3 times a week for 6 weeks under supervision of a physiotherapist after the first evaluation. The subjects in home exercise group were taught exercises and they were informed to do exercises 3 times a week for 6 weeks. Home exercise group was telephoned to motivate them to do exercise or to find out if they have any problem about the exercises once a week for 6 weeks. The exercise programs for each group consisted of these parts: warm up, strengthening, balance and cool down period (Appendix 1). The standard exercises were performed by all of the subjects in each group in order to standardize the exercise procedure. We used OMNI Resistance Exercise Scale for perceived effort to standardize elastic-band (Thera-Band; The Hygenic Corporation, Akron, OH) resistance among subjects (26). Subjects were asked to do 3 repetitions for each exercise starting with lowest resistance elastic band, and the resistance of the elastic band was increased until it reached 5 on the 11-point scale to determine the appropriate elastic band. Second measurements were performed at the end of 6 weeks, the day of routine doctor control for PRP injection. All assessments were performed by the same physiotherapist.

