### **Specific objectives or hypotheses**

The purpose of this study was to compare the effectiveness of supervised physiotherapy and home exercises after PRP injection in patients with knee OA. We hypothesized that the supervised physiotherapy program would be more effective in decreasing pain and improving muscle strength, physical function, and quality of life than home exercises following PRP injection in patients with knee OA.

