#### **Eligibility criteria for participants.**

Inclusion Criteria:

- PRP injection due to knee OA,
- The PRP injection is given at least three days ago,
- 45- 70 years old
- Grade 2-3 according to Kellgren Lawrence osteoarthritis classification

Exclusion Criteria:

- Being male
- Have a neurologic, oncologic and/or rheumatologic disease

- Having any intra-articular application and / or physiotherapy and rehabilitation in the last 6 months,
- Have any other orthopedic problems involving the lower extremities
- having cognitive problem

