### **Statistical Analysis**

A two-way repeated-measures analysis was initially used to investigate differences in the primary outcome variable (muscle strength) between the supervised physiotherapy group and home exercise group over 6- week period; followed by secondary outcomes measures (VAS, WOMAC ). In the occurrence of significant main or interaction effects, a Bonferroni post hoc correction was used to assess significant findings between the groups at specific assessment time points. Statistical analysis was performed using SPSS software (version 22.0). The significance level was set at an alpha of 0.05.

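### No collection of adverse events is described, and the one stated enquiry about problems is made in the home arm only, so any harms count would not be like for like

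*Combined protocol and SAP*

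**What the plan says.** The hypothesis concerns effectiveness only. Under Specific objectives or hypotheses, supervised physiotherapy is expected to be "more effective in decreasing pain and improving muscle strength, physical function, and quality of life than home exercises". No safety objective is stated.

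The measurement sections cover VAS pain, muscle strength, chair stand and stair climb, and WOMAC. Statistical Analysis takes muscle strength as primary, "followed by secondary outcomes measures (VAS, WOMAC"). None of these sections defines, collects, grades or analyses an adverse event.

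On contact with patients, Interventions says of one arm: "Supervised physiotherapy group performed exercises 3 times a week for 6 weeks under supervision of a physiotherapist after the first evaluation". Of the other it says: "Home exercise group was telephoned to motivate them to do exercise or to find out if they have any problem about the exercises", with one call in each of the 6 weeks. It does not say whether the answers are written down, and it gives no matching question for the supervised arm. The outcome measures are then repeated once: "Second measurements were performed at the end of 6 weeks, the day of routine doctor control for PRP injection".

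The eligibility criteria set the earliest entry after injection: "The PRP injection is given at least three days ago".

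**The concern.** Both arms do elastic-band strengthening and balance work, and patients may enter from three days after an injection. They are women aged 45 to 70 with Kellgren-Lawrence grade 2 or 3 disease. The exercises are standardised across arms, so the main difference between the programmes is whether a physiotherapist is present. A reader choosing between them will want to know whether anyone fell, had a swollen knee or had to stop, and in which arm.

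Followed as written, the plan gives no such data on a common basis. If the investigators later assemble a count from memory or clinic notes, it will mix true risk with how often each arm was seen and whether anyone asked. An unplanned statement that no harms occurred would have the same weakness.

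**Working it through.** The plan gives no figure for harms, so there is none to reproduce. Its total of 28 comes from an efficacy calculation and is used here only as a denominator. The check has three steps.

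**1. Opportunities for ascertainment (from Interventions)**

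| | Supervised arm | Home arm |
|---|---|---|
| Planned contacts | 3 per week × 6 weeks = 18 sessions | 1 per week × 6 weeks = 6 calls |
| Type | In person, during exercise | Telephone |
| Stated question about problems | None | Yes, as an alternative to motivating |
| Stated recording of answers | None | None |

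The arms differ in opposite ways: one has more contacts and direct observation, the other has the only stated question. The ratio 18/6 = 3 compares planned contacts. It is not a ratio of detection probabilities, because a patient can report last week's fall at the next weekly call. The net direction of bias cannot be worked out from the documents.

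**2. What the planned outcomes can and cannot show**

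Pain is covered in both arms: "Visual Analog Scale was used to assess the subjects' pain during rest and activity". WOMAC adds pain and stiffness subscales. Both are taken at the first evaluation and at 6 weeks.

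- Worsening that persists to week 6 can be compared by arm.
- A flare or effusion that settles before week 6 can be missed.
- A fall, a session stopped early or an unplanned visit is not an item that the plan describes measuring.

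**3. What 14 per arm could support if harms were recorded identically**

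Patients per arm at 1:1 allocation: 28/2 = 14. All event rates below are assumptions, since the documents give none.

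- Upper limit after 0 events in 14, one-sided 95%: 1 − 0.05^(1/14) = 0.193, or 19.3%. As the upper end of a two-sided 95% interval: 1 − 0.025^(1/14) = 0.232, or 23.2%.
- Chance of at least one event in an arm, 1 − (1 − p)^14: 51% at p = 5%, and 77% at p = 10%.
- Power for 10% against 30%: 14% with Fisher's exact test, 26% by the normal approximation. For 80% power, 62 patients per arm would be needed.
- With no events in one arm, the other needs 5 of 14 before Fisher's p falls below 0.05 (p = 0.041).

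Events are therefore plausible enough to be worth recording, but a formal comparison between arms would tell the reader very little.

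**The case against.** The strongest reply is that this is an efficacy trial of 28 patients with no safety objective, and that perfect recording would still not let it compare safety. That stands. A reader might infer that the missing records cost the trial a safety comparison it would otherwise have had. The figures above do not support this, because the sample size rules out a formal comparison in any case. What is lost is a descriptive account on a common basis.

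Three other tempting readings also go too far.

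- *The home arm's answers are discarded.* The plan is silent on recording, and silence does not show that nothing is written down. The wording of the call also leaves open whether problems are raised every time, and a problem with an exercise may mean technique or adherence rather than harm.
- *Events are three times as likely to be noticed under supervision.* This treats contacts as detections. The scripted question in the other arm pulls the opposite way.
- *The trial will say nothing about harm.* VAS and WOMAC in both arms do speak to lasting symptom worsening.

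It can also be said that patients attend a routine medical check on the day of the second measurement, with no distinction by arm. That is a possible common source, but no section says that the visit supplies trial data. Appendix 1 is not in the text reviewed. It is cited for the content of the exercise programme, so it is unlikely to hold a harms procedure.

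None of this answers the remaining point: no collection of adverse events is described, and the one stated enquiry is made in one arm only.

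**Conclusion.** The concern holds as a gap in the collection and reporting of harms. Events such as falls, short flares, swelling and stopped sessions have no described place in the data, and the arms differ in both contact (18 against 6 planned) and questioning. Any later count by arm would carry bias of unknown direction, which could not be corrected afterwards.

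The planned tests of strength, pain and WOMAC are untouched, and the efficacy hypothesis is not put in doubt. The point is still worth acting on: the exercise is resisted, half the patients do it without a physiotherapist present, and common recording needs no new visits.

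The conclusion assumes that the outcome, intervention and analysis sections describe all planned data collection, and that 28 patients are split 14 and 14 with no dropout.

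**What to change.** Add one short fixed checklist with five items: fall, knee swelling, increase in knee pain, session stopped early, unplanned visit. Ask it once a week in both arms, at the existing call in the home arm and at one existing session in the supervised arm. Record the answers. Report the number of patients with any event by arm, descriptively and without a significance test.

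The cost is six entries per patient, at most 6 × 28 = 168 in all, and a few minutes per patient per week. Some asymmetry will remain. The other 18 − 6 = 12 supervised sessions still allow direct observation, and a session stopped early is seen in one arm but self-reported in the other. The report should say so.

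The documents mix future and past tense, so the contacts may already be over. In that case, state that harms were not systematically collected and draw no conclusion on the comparative safety of the two programmes.

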### **Statistical Analysis**

A two-way repeated-measures analysis was initially used to investigate differences in the primary outcome variable (muscle strength) between the supervised physiotherapy group and home exercise group over 6- week period; followed by secondary outcomes measures (VAS, WOMAC ). In the occurrence of significant main or interaction effects, a Bonferroni post hoc correction was used to assess significant findings between the groups at specific assessment time points. Statistical analysis was performed using SPSS software (version 22.0). The significance level was set at an alpha of 0.05.

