## **Introduction**

### **Scientific background and explanation of rationale.**

Osteoarthritis (OA) of the knee is a chronic disease characterized by pain, reduced range of motion, instability and effusion in the joint. The weakness of the quadriceps as well as the hip muscles are commonly seen symptoms (1). Although the primary effects of the disease occur in articular cartilage; osteophytes, subchondral sclerosis, and cyst formation are concomitant complications to cartilage degradation (2). Progressive deterioration of the joint and chronic pain limit to perform knee functions, which result with a decline in quality of life in knee OA patients.

Physical therapy applications, exercise therapy, pharmacological treatments and intra-articular injections are considered as effective methods to relieve the symptoms of knee OA patients (3). Recently, Platelet-rich Plasma (PRP) treatment has received much attention for its use in the treatment of knee OA (4, 5). It has been shown that PRP injection would reduce pain and improve knee functions in patients with knee OA in the available literature, but some studies are underpowered or unblinded, thus the findings have low reliability. A number of systematic reviews and meta-analyses' evidence have not been exactly comprehensive and are even sometimes controversial (6-9). Because previous studies differed in the concentrations of leucocytes used for the preparation (11) SEP of PRP, dosage schedules, and so on. Moreover, no study has investigated the effect of PRP in comparison with that of a placebo injection in the same patient with bilateral knee OA. It is of interest to examine the effect of PRP in the same patient with bilateral OA.

After PRP injection, patients with knee OA are recommended to exercise.(16). It is thought that home exercises combined with PRP treatment may be an effective approach in the treatment of knee OA, but the importance of performing exercise program under the supervision of a

physiotherapist is emphasized (16). Isokinetic training under the supervision of a physiotherapist had significant effects on pain, function and muscle strength in OA patients after PRP injection (17). However, the combination of PRP injection and exercise therapy under the guidance of a physiotherapist has yet to be established.

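### The primary outcome is named only as muscle strength, but three strength values are recorded per patient and no rule says which of them carries the primary claim

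*Combined protocol and SAP*

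**What the plan says.** The Statistical Analysis section uses a two-way repeated-measures analysis to "investigate differences in the primary outcome variable (muscle strength) between the supervised physiotherapy group and home exercise group" over 6 weeks. Pain and WOMAC come next, as "followed by secondary outcomes measures". On error control it says "The significance level was set at an alpha of 0.05" and that, after a significant main effect or interaction, "a Bonferroni post hoc correction was used to assess significant findings between the groups at specific assessment time points".

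The Muscle Strength Measurement section shows that strength is three variables: "Quadriceps, hamstring muscles and the hip stability isometric test (HipSIT) strength were measured with a hand-held digital dynamometer". Each has its own test position and dynamometer placement, and a value is kept for each: "Each measurement for each muscle was performed 3 times at 30 sec intervals and the higher value was recorded". No sum, mean or index across the three is defined.

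The hypothesis is no more specific. Supervised physiotherapy "would be more effective in decreasing pain and improving muscle strength, physical function, and quality of life than home exercises".

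**The concern.** A primary outcome should lead to one answer. Here one label covers three variables, and two analysts following the same text could reach different primary conclusions. One might report the quadriceps result, another might require all three, and a third might claim success on whichever muscle reached 0.05. Nothing in the plan rules any of these out.

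Two things are at stake. First, the muscle behind the primary claim can be picked once the results are known. Second, whether the error rate for that claim is 5% depends on a rule that the plan does not state. The choice also affects power, because requiring all three muscles is a much harder test than accepting any one.

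**Working it through.** **Does any text settle the choice?**

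- *Order.* The sequence in Statistical Analysis puts strength ahead of pain and WOMAC. It does not rank the muscles.
- *Bonferroni.* It is tied to comparing groups at time points after a significant effect. It does not adjust across muscles.
- *Rationale.* The background section says "The weakness of the quadriceps as well as the hip muscles are commonly seen symptoms". This is context rather than an outcome definition, and it names two muscle groups.
- *Combination.* HipSIT tests several hip muscles together, but nothing combines HipSIT with quadriceps and hamstrings.

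The text does not settle it.

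**Illustration of the error rate.** The plan gives no figure of its own to reproduce beyond the 0.05.

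Inputs from the documents:
- three measures (Muscle Strength Measurement);
- alpha 0.05 (Statistical Analysis);
- 28 patients (Participants and Methods) at 1:1 (trial design), so 14 per arm;
- two assessments, at baseline and 6 weeks (Interventions).

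Assumptions:
- two-sided tests and normal data;
- equal correlation between the muscles' change scores, from 0 to 0.9;
- a claim made if any one muscle has a significant group-by-time interaction.

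With two assessments, the interaction test equals a two-sample t-test on change, with 14 + 14 − 2 = 26 degrees of freedom.

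For independent measures: 1 − 0.95³ = 1 − 0.8574 = 14.3%.

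For correlated measures, by simulation (200,000 runs per scenario, no true group difference; repeat runs agree within about 0.3 percentage points):

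| Rule | r = 0 | r = 0.5 | r = 0.7 | r = 0.9 |
|---|---|---|---|---|
| Any one of three at 0.05 | 14.3% | about 12.5% | about 11% | about 8.4% |
| All three at 0.05 | 0.01% | 0.3% | 0.8% | 2.1% |
| Holm, at least one passes | 4.9% | 4.5% | 4.0% | 3.0% |

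A single test on the mean of the three changes stays at about 5% at every correlation. The all-three rule cannot exceed 5% even if two muscles truly differ, because the third must still pass its own 5% test.

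**Sensitivity to the other open point.** The plan acts on main effects as well as interactions. The figures below still count any one muscle, and run over between-muscle correlations from 0 to 0.9 and assumed pre-post correlations of 0.5 or 0.8:

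- Group main effect or interaction counts at 0.05: for independent tests 1 − 0.95⁶ = 26.5%, falling to about 16% at r = 0.9.
- Only the 6-week difference counts, at 0.05/2 = 0.025: 1 − 0.975³ = 7.3%, falling to about 4.4%.
- Both a significant interaction and a 6-week difference at 0.025 are needed: between about 0.6% and 1.6%.

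**Power.** The documents give no strength effect, so take a hypothetical difference of 1.10 SD of the change score, chosen because it gives 80% power at 0.05 with 14 per arm. The noncentrality is 1.10 × √(14/2) = 2.91.

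- At 0.05/3 = 0.0167, the first Holm step, power is 63.9%.
- At 0.0167, 18 per arm gives 77.8% and 19 per arm gives 80.5%, so 38 patients in total.
- If all three muscles respond equally, Holm has about 70–74% power per muscle, and the all-three rule has about 51% (r = 0) to 72% (r = 0.9).

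**The case against.** A reader might infer that the plan runs three unadjusted primary tests and so has a 14.3% false-positive rate. The documents do not support that. They describe one repeated-measures analysis of one primary variable. They do not say that there are three separate tests, or that one significant muscle is enough. A composite or an all-three requirement is not excluded, and either would keep error at 5% or less.

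The 14.3% also rests on the interaction alone, whereas the plan acts on main effects too and then adds a Bonferroni follow-up. Depending on how those steps are read, the any-one figure runs from about 1% to about 26%. This objection stands. The error rates illustrate one reading and do not measure this trial's actual error.

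It is also fair that a Holm adjustment alone does not say how many muscles must pass before muscle strength can be said to have improved. A claim rule has to come with it.

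What the objection does not remove is the gap. Every reading that controls the error needs a statement that the plan does not contain, and the separate value kept for each muscle makes a per-muscle analysis the natural one.

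**Conclusion.** The concern holds as under-specification of the primary outcome. One primary variable is named at 0.05, three are recorded, and no rule connects them, so the muscle carrying the claim can be chosen after the data are seen.

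The size is conditional. If any one significant interaction supports the claim, family-wise error is 14.3% for independent measures and still about 8.4% at a correlation of 0.9. The correlations, two-sided testing and the any-one rule are assumptions. The documents do not show that error is in fact inflated. The point should be repaired, and the repair is cheap.

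**What to change.** Before any between-group strength result is examined, name one strength measure (the sponsor's choice) and its group-by-time contrast as the single primary at 0.05, and make the other two secondary. This takes one or two sentences, with no alpha adjustment and no change to the 28 patients.

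If all three are to stay primary, state the claim rule in the Statistical Analysis section, as one of:

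- all three group-by-time contrasts significant at 0.05; or
- Holm across the three group-by-time p-values at an overall 0.05, with the claim limited to the muscles that pass.

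Both lower power, as the hypothetical case above shows: about 64% instead of 80% at the first Holm step, and about 51–72% for the all-three rule when all three muscles respond.

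Much of the document is in the past tense. If between-group strength results have already been seen, a choice of one measure can no longer be called prespecified. In that case, report all three with Holm-adjusted p-values.

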### **Methods**

#### **Description of trial design (such as parallel, factorial) including allocation ratio**

This will be a randomized allocation ratio 1:1, controlled study conducted in the Hacettepe University, Turkey.

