### **Outcome Measures**

### **Participants and Methods**

A randomized control clinic study design was used for the present study. A sample size calculation was conducted using G\*power (v3.1.9.2, Heinrich-Heine-University, Dusseldorf, Germany). An estimated more than 2-point pain level changes on VAS between pre- and posttreatments for repeated measures analysis, a power of 0.80, a  $\alpha$  of 0.05 and a total sample size of 28 knee OA patients need to be included in the present study.

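### The analysis plan names no effect as deciding the between-group hypothesis, and its follow-up 6-week comparison leaves out the baseline value; a baseline-adjusted 6-week difference should be named instead

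*Combined protocol and SAP*

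**What the plan says.** The hypothesis is between groups: under Specific objectives or hypotheses, the "supervised physiotherapy program would be more effective in decreasing pain and improving muscle strength", among other outcomes, than home exercise. The trial design section gives the allocation: "This will be a randomized allocation ratio 1:1, controlled study". There is a first evaluation before the exercises start and one later assessment; Interventions states that "Second measurements were performed at the end of 6 weeks, the day of routine doctor control for PRP injection".

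Statistical Analysis is one short paragraph. A two-way repeated-measures model is applied to muscle strength as the primary outcome, looking for differences "between the supervised physiotherapy group and home exercise group over 6- week period", and then to VAS and WOMAC. The follow-up rule is: "In the occurrence of significant main or interaction effects, a Bonferroni post hoc correction was used to assess significant findings between the groups", taken at individual assessment times. Alpha is 0.05. The paragraph does not say whether the group effect, the interaction or a follow-up comparison answers the hypothesis. It mentions no baseline covariate and no estimated difference with a confidence interval.

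**The concern.** With two groups and two assessments, the plan contains several results that could be read as the answer, and they are different tests.

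- The **group main effect** averages the baseline and 6-week differences. Randomisation makes the expected baseline difference zero, so it estimates half the 6-week effect.
- The **interaction** is the two-sample t-test on change.
- The **follow-up test at 6 weeks** ignores baseline.
- The **follow-up test at baseline** tests a null that randomisation makes true, so it tells us nothing about treatment.

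The wording about change over the 6 weeks points to the interaction. The next sentence then puts main and interaction effects on the same footing and sends the reader to comparisons at single time points. Read literally, a time effect shared by both arms also opens that step, although it says nothing about supervised versus home exercise.

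At stake is whether the conclusion is fixed before the data are seen, and how much information is drawn from a small sample.

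**Working it through.** **Inputs from the documents.** The total is 28 (Participants and Methods: "a total sample size of 28 knee OA patients need to be included in the present study"), which is 14 per arm at 1:1. Alpha is 0.05. There are two assessments. The figure of 28 cannot be reproduced, because no SD, standardised effect or correlation is given and its stated basis is a pre-to-post VAS change. It is used here only as the sample size.

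**Assumptions.** Two-sided tests; equal SDs, scaled to 1; no dropout; a true 6-week difference d; baseline to 6-week correlation r, varied. The plan does not say what Bonferroni divides by; halving alpha over two time points is taken as the alternative.

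**Formula.** Power comes from the noncentral t distribution with noncentrality d/√v × √(14/2), where v is the variance factor:

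- 6-week values only: v = 1, 26 df
- interaction (change): v = 2(1 − r), 26 df
- ANCOVA: v = (1 − r²)(1 + 1/24), 25 df
- group main effect: d/2 in place of d, v = (1 + r)/2, 26 df

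**Worked example, d = 0.8, r = 0.7.**

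- 6-week test: 0.8 × √7 = 2.12 against a critical value of 2.06; power 53%.
- Interaction: v = 0.60, noncentrality 2.73; power 75%.
- ANCOVA: v = 0.51 × 25/24 = 0.531, noncentrality 2.90; power 80%.

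**Power at d = 0.8**

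| r | 6-week test (alpha 0.05 / 0.025) | Interaction | ANCOVA |
|---|---|---|---|
| 0 | 53% / 41% | 30% | 51% |
| 0.1 | 53% / 41% | 33% | 52% |
| 0.2 | 53% / 41% | 36% | 53% |
| 0.3 | 53% / 41% | 41% | 55% |
| 0.5 | 53% / 41% | 53% | 63% |
| 0.7 | 53% / 41% | 75% | 80% |
| 0.8 | 53% / 41% | 90% | 91% |

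The group main effect has 24/22/20/19% at r = 0.3/0.5/0.7/0.8.

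**Gain from ANCOVA at r = 0.3/0.5/0.7/0.8.** Over the interaction: 55.2 − 40.6, 63.4 − 53.1, 79.7 − 74.9 and 91.3 − 89.6, or about 15/10/5/2 points. Over the 6-week test at 0.05 (53.1%): about 2/10/27/38 points.

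**Break-even with the 6-week test.** (1 − r²) × 25/24 = 1 gives r² = 0.04, so r = 0.2. Below that ANCOVA loses 1 to 2 points.

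**Other effect sizes, same four correlations.** At 0.5 SD: 6-week test 25% (16% at halved alpha), interaction 19/25/38/52%, ANCOVA 26/30/42/55%. At 1.0 SD: 72% (61%), 58/72/91/98%, 74/82/94/99%.

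**Validity.** In a simulation of bivariate normal data (100,000 trials per setting), the 6-week test, the interaction and ANCOVA each rejected a true null in 4.9 to 5.1% of trials. At a true 0.8 SD, each gave a mean estimate of 0.80; the group main effect gave 0.40. The written sequence, with the 6-week test run only after a significant main or interaction effect, had null error of 3.3 to 5.1% at 0.05 and 2.0 to 2.6% at 0.025, for shared change from 0 to 1 SD.

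**Agreement.** At 0.8 SD the 6-week test and the interaction reach different conclusions in 32/34/39/43% of trials. With no effect they differ in 8 to 9%.

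**The case against.** The strongest reply is that the interaction is plainly meant. The model is group by time, the text speaks of differences over the 6 weeks, and Participants and Methods refers to a repeated-measures analysis for the sample size. The interaction already uses baseline, so only the follow-up step ignores it. ANCOVA's advantage over the interaction is then the smaller set of figures (15/10/5/2 points), and one sentence naming the interaction would close the question of which effect counts. All of this stands, except that the documents never say that the interaction decides, and the follow-up rule points elsewhere.

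The disagreement rates also need care. At a true 0.8 SD effect they mostly reflect one low-powered valid test missing a real effect. ANCOVA and the interaction themselves disagree in 24/19/11/5% of such trials.

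A reader might infer that the plan inflates type I error. Counting either the group main effect or the interaction as success would give 1 − 0.95² = 9.75% per outcome. The text does not state that rule, although it does not exclude it: it says that a significant effect leads to a further comparison. Run literally, that sequence does not inflate the error of the 6-week test. A reader might also infer bias from the missing covariate; under randomisation there is none.

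**Conclusion.** The point holds as a gap in specification and a loss of precision. Nothing in the documents names the deciding effect or plans a baseline covariate, and that finding rests on no numerical assumption.

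The size of the gain does rest on assumptions: 14 per arm, equal SDs, normal data, and values for d and r that the documents do not supply. On those terms ANCOVA has more power than every test in the written plan from about r = 0.3 upward, is level with the unsplit 6-week test near 0.2, and is slightly worse than it below that. The gain over the interaction is largest at low r; the gain over the 6-week test is largest at high r.

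It would be too much to say that ANCOVA settles the primary result. Muscle Strength Measurement lists three measures ("Quadriceps, hamstring muscles and the hip stability isometric test (HipSIT) strength were measured with a hand-held digital dynamometer"), and none is singled out as primary. This is worth correcting, but it does not invalidate the trial.

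**What to change.** Replace the main-effect trigger and the follow-up rule with:

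> The treatment effect is the between-group difference at 6 weeks from ANCOVA with the baseline value of the same measure as covariate, reported with 95% CI.

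Use the same model for every outcome, and drop the between-group test at baseline. If repeated-measures ANOVA is kept, state that the group-by-time interaction alone decides the hypothesis. That settles which effect counts; ANCOVA adds precision.

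The cost is a few sentences and one degree of freedom, with no new patients, visits, data or software. If r is near 0, up to about 2 points of power are lost. The trial design section is in the future tense, while Interventions and Statistical Analysis are in the past tense. If the data have already been analysed, record the change as a dated amendment and report the original analysis alongside. The choice among the three strength measures needs its own statement.
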